impairment and treatment retention are both improved, while **The Secondary Objective** is to replicate the our preliminary finding of negative impact of cognitive symptoms of ADHD on PTSD clinical outcomes. **The Tertiary Objective** is to assess the efficacy of ATX in reducing broad spectrum of PTSD symptoms. The proposed study will take 10 weeks and include two phases (**Phase I**: Initial Phase, 5 weeks; **Phase II**: Crossover Phase, 5 weeks). The crossover design was employed to both achieve study objectives while minimizing costs. Each phase consists two periods: **Period I** (week1 in Phase I and week6 in phase II) consist of psychological and physical assessments and placebo lead-in/wash-out, in which subjects take 6 days placebo; **Period II** (weeks 2-5 in Phase I and week7-10 in Phase II) consist of treatment with either atomoxetine 80mg daily or placebo daily). This project will take advantage of established on-going PTSD assessment and treatment clinical trials currently performed at the Ralph H. Johnson VA Medical Center (RHJVAMC) to facilitate recruitment. The proposed 50 veterans with ADHD/PTSD will be recruited from these on-going trials enabling both comprehensive assessment and evaluation of patients' engagement in ongoing PTSD treatments. Subjects will be randomized and assigned by the study investigator ([name]) into crossover group 1 (ATX at Phase I, then placebo at Phase II) or 2 (placebo at Phase I, then ATX at Phase II) with both placebo and medication administered through pharmacy. Subjects and other investigators are thus able to remain blinded to the order of treatment assignment throughout the study. The 1-week interval was based on published pharmacokinetic data for 4 week doses of ATX (*Witcher et al, 2003*). After crossover, patients will be unblinded and data will be cleaned and analyzed. Final follow up will be 30-days after last visit.

C2. Investigational Agent: ATX is a non-stimulant, FDA approved agent for treatment of ADHD. ATX 80mg is the most common adult dose used in ADHD with and without comorbid condition (Adler et al, 2009). In this project, 80 mg ATX and placebo will be prepared in capsules with identical appearance and similar taste by Eli Lilly and Company, Indianapolis, Indiana.

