Conners' Adult ADHD Rating Scales-Self-Report: Short Version (CAARS-S:S, Conner et al, 1999): The CAARS-S:S is a 26-item questionnaire that assesses symptoms of ADHD in persons aged ≥18 years. T-scores above 65 indicate a likelihood of moderate to severe ADHD symptoms and impairment.

The Adult ADHD Quality of Life-29 (AAQOL-29, Brod et al, 2006): AAQoL-29 is a participant-reported outcome measure used to examine disease specific functional impairments and quality of life for adults with ADHD. The AAQOL-29 includes Life Productivity, Psychological Health, Quality of Relationships, and Life Outlook subscales. Higher scores on the AAQOL-29 indicate better functioning.

The Barkley Adult ADHD Rating Scale-IV (BAARS-IV, Barkley, 2011): BAARS-IV offers an essential tool for assessing current ADHD symptoms and domains of impairment and recollections of childhood symptoms. BAARS-IV is empirically based, reliable, and valid for diagnosis and cognitive evaluation of adult ADHD.

Response Inhibition Task: The Go-NoGo (GNG) and Stop-Signal Task (SST) are classical paradigm to investigate response inhibition and response execution (higher-order motor and attention control) processing, and a reliable marker reflecting medial prefrontal functioning (Fallgatter and Strik, 1999). Further, ATX has been found to improve GNG and SST performance in ADHD patients (Nandam et al 2014; Chamberlain et al, 2007). GNG/SST require participants to implement their response to one kind of stimuli (Go/Start) and to withhold the responses to the other kind of stimuli (NoGo/Stop). Therefore, GNG commission errors SST time are a reliable marker to examine individual executive function and to measure ATX treatment response. GNG and SST will be performed at [name] TMS Laboratory.

Table 1: Outline of study procedures and assessments of the study.

Initial Assessments	Screening/ Baseline	Phase I Start	Phase I Treatment visit	Phase I Follow up, Crossover lead in	Phase II Start	Phase II Treatment visit	Phase II Follow up	Final Follow up visit
visit (week)	1	2 (W1)	3 (W2)	4 (W5)	5 (W6)	6 (W7)	7 (W10)	8 (W14)
Consent	X							
MINI	X							
CAADID Part II	X							
CES	X							
DTS	X							
CGI-S	X							
CGI-I			X	X	X	X	X	
CAARS-S:S	X	X	X	X	X	X	X	X
BAARS	X			X			X	X
AAQoL-29	X			X			X	
SF-36-V	X			X			X	
CAPS-IV	X			X			X	
Ham-D	X		X	X	X	X	X	X
Ham-A	X		X	X	X	X	X	
GNG/SST	X			X	X		X	
Vital Signs	X	X	X	X	X	X	X	
Labs, EKG	X		X			X		
UDS	X			X				
Dispense med		X	X		X	X		
Compliance			X	X	X	X		

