Concom meds	X	X	X		X	X		
AEs			X			X		

Safety assessments: At each study visit, safety will be assessed by measuring: weight, sitting blood pressure, heart rate, adverse events (except baseline), and use of concomitant medications. Laboratory and EKG assessments will be performed at baseline, one and seven weeks. Anxiety, depression, and suicidal ideation will be assessed with Ham-A, Ham-D, and suicide screen in each of the visits. Compliance will be assessed by pill counts and appointment attendance. Referrals to the Charleston PTSD clinic will be conducted at the final study visit for any remaining PTSD symptoms and the CBT clinic for remaining ADHD symptoms.

Follow-up: The final visit, 30-days after study completion, will include safety assessments, along with follow-up of any unresolved adverse events. This visit will also provide assurance that veterans who participated in this medication study will have adequate follow-up care in the Charleston VAMC PTSD or Mental Health Outpatient Clinic either with continued medication or psychotherapy. This visit may be done over the phone or by mail.

Diagnostic Procedures: After obtaining the informed consent, a trained research assistant will perform the initial interview and administer all of the diagnostic scales to the participants. [name], [name] (MD, Co-Investigator) and [name] (PI) will make the final diagnosis based on all the data collected. The DSM-IV diagnostic criteria will be used to ascertain each phenotype.

Database Management: All collected clinical, demographic, and geographic data will be stored in Research Database Storage in the Charleston VAMC PTSD Program. The genotyping data will be stored in [name] laboratory Research Database. For each patient, the clinical database will provide information as following: age, gender, ethnic origin, medical and psychiatric diagnosis, family history, developmental history, and existence of comorbidity. The genotyping data will be separately entered without knowledge of clinical data. Strict confidentiality is maintained regarding database information, which is secured and for research purposes only. All the specimens from the subjects will be labeled by code at the clinic. Names will not appear on specimens, nor will they be available in the laboratory. The person conducting the genotyping is blind to the clinical profile of the subject. No names or identifiable information will be used in any data presentation.

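### Table 1 marks fewer adverse-event and concomitant-medication checks than the safety text requires, and no compliance check follows the W7 dispensing

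*Combined protocol and SAP*

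**What the plan says.** Section C3, under the safety assessments, sets an every-visit rule: "At each study visit, safety will be assessed by measuring: weight, sitting blood pressure, heart rate, adverse events (except baseline), and use of concomitant medications". The same paragraph adds: "Anxiety, depression, and suicidal ideation will be assessed with Ham-A, Ham-D, and suicide screen in each of the visits". The follow-up paragraph covers the last contact: "The final visit, 30-days after study completion, will include safety assessments, along with follow-up of any unresolved adverse events". It allows that contact to be by phone or mail.

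The visit schedule is headed "Table 1: Outline of study procedures and assessments of the study" and has eight visit columns: baseline, W1, W2, W5, W6, W7, W10 and W14. The relevant rows are marked as follows.

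- Adverse events: W2 and W7.
- Concomitant medications: baseline, W1, W2, W6 and W7.
- Dispensing: W1, W2, W6 and W7.
- Compliance: W2, W5, W6 and W7.

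On compliance, section C2 asks participants to bring back unused tablets and empty vials, and section C3 names pill counts and attendance as the methods. Neither passage names a visit. Section C1 makes weeks 1 and 6 a "placebo lead-in/wash-out, in which subjects take 6 days placebo" and puts randomised treatment in weeks 2-5 and 7-10.

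**The concern.** The protocol gives two safety schedules that disagree, and does not say which one governs. Coordinators often build visit checklists from the schedule table. If that happens here, no adverse-event enquiry is made at W5 or W10, the visits that close the two treatment periods, and none is made after W7.

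Both adverse-event marks fall on dispensing visits. If W1 and W6 supply the placebo week and W2 and W7 the treatment supply (our reading; the table does not say), both enquiries fall at the start of a treatment period.

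Safety is part of the stated purpose in section C1, and safety measures are secondary outcomes in the statistical section. Concomitant medications matter because interacting drugs are an exclusion and participants are asked to keep existing medication stable.

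The compliance gap is a separate matter. It contradicts no sentence, but it leaves the Phase II treatment supply without a marked check while the Phase I supply has one. That is uneven for a crossover comparison.

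**Working it through.** The plan gives no figure to reproduce, so the check is a cell-by-cell comparison of the C3 text with Table 1.

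| Item | BL | W1 | W2 | W5 | W6 | W7 | W10 | W14 |
|---|---|---|---|---|---|---|---|---|
| AEs, text | – | yes | yes | yes | yes | yes | yes | yes |
| AEs, table | – | – | X | – | – | X | – | – |
| Concomitant medications, text | yes | yes | yes | yes | yes | yes | yes | yes |
| Concomitant medications, table | X | X | X | – | X | X | – | – |
| Dispensing, table | – | X | X | – | X | X | – | – |
| Compliance, table | – | – | X | X | X | X | – | – |

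**Column alignment.** The table was read from a PDF, so a column shift had to be considered. Each of the ten rows checked has nine cells (a label and eight visits). The CGI-I row is marked at W2, W5, W6, W7 and W10, which agrees over those visits with the C3 text (all visits except baseline and W1). A shift is unlikely, though it cannot be fully excluded.

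**Adverse events.** Required: 8 − 1 (baseline) = 7. Marked: 2. Missing: 7 − 2 = 5 (W1, W5, W6, W10, W14). No study product is dispensed before W1; setting that visit aside gives 2 of 6. End-of-treatment visits marked: 0 of 2.

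**Concomitant medications.** Required: 8. Marked: 5. Missing: 8 − 5 = 3 (W5, W10, W14). End-of-treatment visits marked: 0 of 2.

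**Together.** Required: 7 + 8 = 15. Marked: 2 + 5 = 7. Missing: 15 − 7 = 8.

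**Compliance.** Each dispensing visit was matched to the next compliance mark:

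- W1 supply: checked at W2.
- W2 supply: checked at W5.
- W6 supply: checked at W7.
- W7 supply: no later mark; W10 and W14 are blank.

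**What a table-only schedule would capture.** An event arising after W2 in Phase I would next be asked about at W7, after the crossover and the placebo week. It could still be recorded, but late. An event arising after W7 in Phase II would meet no further marked enquiry. The gap from W7 to W10 is the same in both sequences, with atomoxetine in one and placebo in the other.

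**The case against.** The strongest reply is that the text already states the fuller rule and the follow-up paragraph repeats it for the last visit. The table calls itself an outline and has no row for the suicide screen that the text requires at every visit, so a blank cell cannot be read as an instruction to skip. Every consequence therefore depends on staff working from the table, which the documents do not say they will do. This stands, and it is why the point is minor. It does not remove the disagreement: the table has dedicated rows for both items with visit-specific marks, and vital signs, governed by the same sentence, are marked at W5 and W10.

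A second reply is that the compliance item contradicts nothing: no visit is named for pill counts, the return instruction covers all unused tablets, and W10 attendance itself counts towards compliance. This also stands. The item is a missing mark that needs clarifying.

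Third, the raw counts can overstate the gap. W1 precedes any product, the W7 enquiry could still pick up Phase I events, and vital signs, Ham-A and Ham-D are all marked at W5 and W10. These points are fair; the real exposure is Phase II after W7.

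Finally, nine marks would not bring the whole table into line with the text. Vital signs are unmarked at W14, Ham-D at W1, and Ham-A at W1 and W14. That is correct, and the proposed change is limited to the three rows discussed here.

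**Conclusion.** The concern holds, as a minor inconsistency. Table 1 leaves 8 of the 15 adverse-event and concomitant-medication cells required by the text unmarked, including all four at the two end-of-treatment visits (two items × two visits). It also has no compliance mark after the W7 dispensing.

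The counts rest on the table columns having been read correctly. The practical consequence rests on the further assumption that the table is used as the working schedule. In that case adverse-event capture is less sensitive, most clearly from W7 to W10, and Phase II treatment compliance has no marked check. If staff follow the text, adverse events and concomitant medications are collected in full, and the Phase II pill count depends on the general return instruction. The amount of safety information that would be lost cannot be estimated from the documents. Efficacy estimates are unaffected, and the gap does not by itself favour either treatment.

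**What to change.** Amend three rows of Table 1:

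- Adverse events: add W1, W5, W6, W10 and W14 (5 marks). W5, W10 and W14 matter most; W14 can be done by phone or mail.
- Concomitant medications: add W5, W10 and W14 (3 marks).
- Compliance: add a pill count at W10 (1 mark).

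That is 5 + 3 + 1 = 9 marks, at a cost of a few minutes at visits already planned. No new visit, laboratory test, EKG or analysis is needed.

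While the table is open, the sponsor could also settle the laboratory and EKG week, which the text gives as weeks one and seven and the table as W2 and W7. This may be only a labelling difference, and the finding does not depend on it.

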PTSD Medication Stabilization: Those patients meeting inclusion criteria will be asked to maintain medications at current dosages where medically possible. Participants who have not initiated new prescription medications in the previous 4 weeks will initiate treatment one week following the assessment battery. However, those potential participants who have recently begun trials of prescription medication will be required to wait 4 weeks post-assessment to ensure medication stabilization, at which point the assessment battery will be re-administered.

Efficacy Assessments and Outcome Measurement: Primary outcome measures will be conducted at baseline and all subsequent visits by a qualified research clinician using the CAARS-S:S, with the Barkley Adult ADHD Rating Scale-IV (BAARS-IV) and Adult ADHD Quality of Life-29 (AAQoL-29) conducted at follow up visits. Clinical Global Impression Severity (CGI-S, at baseline only) and Clinical Global Impression Improvement (CGI-I, at all visits except baseline and W1) will be done as well. Additional assessments for evaluating secondary outcomes will include the Clinician Administered PTSD Scale (CAPS), Hamilton Depression Scale (HAM-D). Quality of life will be assessed using the Veteran's version of the Medical Outcomes Study 36-Item Short-Form Health Survey (SF36-V). In addition to subjective measures, the response inhibition task Go/NoGo (GNG) and Stop Signal (SST) will be used as objective assessments to measure ATX treatment outcomes.

Key Assessment Measures:

Mini-International Neuropsychiatric Interview (MINI, Sheehan et al., 1998): The MINI is an abbreviated structured psychiatric interview that takes approximately 10-20 minutes to complete. The MINI has shown good inter-rater reliability and test-retest reliability for screening psychiatric disorders.

CAADID Part II: Diagnostic Criteria (CAADID, Epstein et al., 2001) The CAADID is a structured interview that assists in the process of diagnosing adult ADHD. This assessment is appropriate for those 18 and older. It is most effective when used with other types of ADHD measures, such as the CAARS™.

Clinician Administered PTSD scale (CAPS, Weathers et al., 2000): The CAPS is a structured interview that assesses both frequency and intensity of PTSD symptoms according to DSM-IV criteria. It provides both a dichotomous index for PTSD diagnoses and a continuous index of PTSD symptom severity.

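### The safety text and Table 1 disagree on the first post-baseline laboratory/EKG test (week 1 or W2); if the text is followed, ATX-first patients have no such test while on ATX

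*Combined protocol and SAP*

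**What the plan says.** Two places in section C3 set the laboratory and EKG schedule.

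- **Text (Safety assessments):** "Laboratory and EKG assessments will be performed at baseline, one and seven weeks".
- **Table 1 (laboratory/EKG row):** ticks at Screening/Baseline, W2 and W7. W1, W5, W6, W10 and W14 are blank.

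Section C1 fixes what patients take in each week. Weeks 1 and 6 "consist of psychological and physical assessments and placebo lead-in/wash-out, in which subjects take 6 days placebo". The randomised periods are "weeks 2-5 in Phase I and week7-10 in Phase II) consist of treatment with either atomoxetine 80mg daily or placebo daily". Group 1 takes ATX in Phase I and placebo in Phase II; group 2 takes them in the reverse order.

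The other relevant Table 1 rows are dispensing ("Dispense med X X X X", at W1, W2, W6 and W7) and vital signs ("Vital Signs X X X X X X X", at every visit from baseline to W10). The W2 and W7 columns are headed as treatment visits, and adverse events are ticked only there.

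The baseline evaluation in section C3 itemises the safety tests: EKG, liver and renal panel, blood count and urine toxicology. Table 1 does not itemise the later laboratory tests.

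**The concern.** Site staff cannot follow both schedules, and the choice decides whether one treatment sequence is tested on drug at all. Section 1.1 c lists QT prolongation and severe liver injury among the serious risks of ATX, and section C3 counts the safety measures as secondary measures. A week-1 test is a second pre-ATX test for everyone. If it replaces the W2 test, the ATX-first group is left with one later test, taken when ATX has already stopped. That test could still show a lasting laboratory change, but it is not an on-drug EKG. No later laboratory or EKG test is scheduled, and the W14 contact may be remote.

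**Working it through.** **1. Can the two schedules be the same schedule counted differently?**

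Spacing of the two post-baseline tests:
- text: 7 − 1 = 6 weeks
- Table 1: 7 − 2 = 5 weeks

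A shift of origin changes both test times equally and leaves the spacing alone, so it cannot reconcile them. Converting the table's W2 and W7 confirms this:

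| Weeks counted from | Table 1 tests fall at | Equal to 1 and 7? |
|---|---|---|
| Study-week label | 2 and 7 | No |
| The W1 visit | 1 and 6 | No |
| A baseline one week before W1 | 2 and 7 | No |
| Start of randomised treatment (W2) | 0 and 5 | No |

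The third row takes up the statement in section C3 that stable patients "will initiate treatment one week following the assessment battery".

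**2. Which visits does the text point to?**

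The post-baseline visits are W1, W2, W5, W6, W7, W10 and W14. The only pair six weeks apart is W1 and W7. Counted from the W1 visit, the text would mean W2 and W8, and there is no W8 visit. The text therefore lands on scheduled visits only as W1 and W7.

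**3. What is each patient taking at those tests?**

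Assumptions: day 1 is the start of week 1, and weeks have 7 days. ATX is then taken on days 8–35 (ATX-first) or days 43–70 (placebo-first). The visit day within the week is not given, so the start and end of the week are both shown.

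| Test | ATX-first | Placebo-first |
|---|---|---|
| Week 1 (days 1–7) | 0 ATX days so far | 0 ATX days so far |
| W2 (day 8 to day 14) | 0 to 6 prior ATX days | 0 ATX days so far |
| W7 (day 43 to day 49) | off ATX since day 35 | 0 to 6 prior ATX days |

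Under the text (W1 and W7), ATX-first patients have no test on ATX, whichever day of the week the visits fall on. At W7 they have been off ATX for at least 43 − 35 − 1 = 7 full days. Under Table 1 (W2 and W7), each sequence has one test in a scheduled ATX week. Whether that test follows a dose depends on the order of testing and dosing at the visit.

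**4. How many patients?**

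The statistical section aims for 40 completers. No allocation ratio is given.
- Equal allocation (assumed): 0.5 × 40 = 20 ATX-first patients.
- Splits from 40:60 to 60:40: 0.4 × 40 = 16 to 0.6 × 40 = 24.
- The 50 patients in the same section are a ceiling on consent, so 0.5 × 50 = 25 is an upper bound under equal allocation, not an expected number.

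**The case against.** The best defence is that Table 1 is the working schedule, that it places a test in an ATX week for each sequence, and that the sentence in the text is a slip. ATX is an approved drug given at a usual adult dose. Vital signs are ticked at W5 and W10, so blood pressure and heart rate are measured on ATX in both sequences. All of this stands, and it keeps the point minor. It does not make the text harmless, because a site that follows the sentence omits the only on-ATX test of one sequence. Adverse-event collection is a weaker reassurance: the text says "safety will be assessed by measuring: weight, sitting blood pressure, heart rate, adverse events (except baseline") at each visit, but Table 1 ticks adverse events only at W2 and W7.

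A reader might infer something stronger: that the W2 and W7 tests are pre-dose, so that nobody in either sequence has an EKG or laboratory test on ATX. The dispensing row gives some support, since four dispensing visits match the four supply periods, and randomised drug would then be first handed out at W2 and W7. But those visits are labelled as treatment visits, adverse events are ticked there, and section C1 places both weeks inside the randomised periods. The table is also too incomplete to carry fine inference: compliance is not ticked at W10, and concomitant medication is not ticked at W5 or W10 although the text asks for it at each visit. No section states the order of testing and dosing. The documents support 'not assured', not 'never done'.

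A reader might also infer that the tests belong at W5 and W10. No section requires a test late in treatment, and moving them has a clinical price, so the documents do not settle that either.

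**Conclusion.** The concern holds as an inconsistency in the safety schedule. The text and Table 1 agree on baseline and week 7 and conflict on the first post-baseline test, and no counting convention removes the conflict. If the text is followed, the ATX-first group has no EKG or laboratory test on ATX: about 20 of 40 completers under assumed equal allocation (16 to 24 for the splits shown). If Table 1 is followed, each sequence has a test in an ATX week, but the documents do not say whether it comes after the first randomised dose.

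One further assumption applies: the laboratory tests at W2 and W7 are taken to include the liver and renal panel named at baseline. The point is minor and does not touch the efficacy analysis. It is more than clerical, because correcting the sentence changes which safety test is done.

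**What to change.** In section C3, Safety assessments, replace the post-baseline times with W2 and W7 so that the text matches Table 1. Add a clause saying that the W2 and W7 tests are done after randomised dosing in that period has begun. It would help to state in the same place which laboratory tests are repeated. Table 1 needs no change. The cost is one edited sentence and one added clause, with no extra test or visit.

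If the tests cannot follow the first randomised dose at W2 and W7, the investigators could consider the existing W5 and W10 visits. On the same day count, each sequence would then have one test after 21 to 27 days of ATX. The downsides are that there is no early test in either treatment period and that results arrive as dosing ends, when they can do little to guide stopping the drug. That is a clinical choice.
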